7.5 Study Duration

- 1) The duration of the whole PMOS is estimated to be about 4 years.

- Study start: September 2012
-

- Recruiting phase: September 2012 - December 2014
 - Data completion: January 2018
 - End of study: The date on which statistical analysis dataset for Clinical Study Report becomes available
 - Data analysis and final report: April 2018 – October 2018
- 2) For each individual patient, the PMOS starts with the enrollment at the beginning of the treatment with adalimumab.
- Observation period
 - 104 weeks (or discontinuation of this study)
 - Discontinuation of this study
 - Patients within 52 weeks into this study: When adalimumab treatment is discontinued.
 - Patients after 52 weeks into this study: When any biologics other than adalimumab is administered.

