Treatment period (day) Completion date of treatment *Per record	
It should be between the start date of Humira treatment and the completion date of treatment per treatment record.
 
When the completion date of treatment in the information on the previous treatment within the same CRF and the start date of treatment in the information on the relevant treatment are the same date, the completion date of treatment in the information on the previous treatment should be - 1 day.
 
The records with the dose of 0 mg should be excluded from the analysis.

Dosing intervals (day) *Per record	Biweekly should be 14 days, once in three weeks should be 21 days, and once in four weeks should be 28 days, respectively.
Total number of doses	The total after calculating the number of doses per record by rounding up the first decimal place should be taken for treatment period (day)/dosing intervals (day).
Patients who discontinued Humira treatment	If the final fixed CRF is the first or second CRF, the patients should be handled as the patients with a description in the “treatment discontinuation” column in the final CRF. If the final fixed CRF is the third CRF, the patient should be handled as the patients with a description of the completion date of treatment in the final record of the “Humira treatment status” column in the final CRF.
Patients who are continuing Humira treatment	If the final fixed CRF is the first or second CRF, the patients should be handled as the patients without a description in the “treatment discontinuation” column in the final CRF. If the final fixed CRF is the third CRF, the patient should be handled as the patients with a description of “continuing” in the final record of the “Humira treatment status” column in the final CRF.
Date of treatment discontinuation	In patients who discontinued Humira treatment, the completion date of Humira treatment should be the date of discontinuation.
Low body weight	Patients with body weight of < 30 kg.
Date of survey discontinuation	It should be the date of survey discontinuation described in the third CRF. It should be the start date of treatment with other biological products, or the older date among the last follow-up date.
AE follow-up period	It should be between the date of initial Humira treatment and the date of initial Humira treatment + 755 days.

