Reason for discontinuation (third CRF)	Occurrence of AEs, symptom improved, inadequate response, patient refused treatment with Humira, others (pregnancy/desire for pregnancy, others), undescribed
Reason for survey discontinuation	Administration of biological products other than Humira, failed to visit hospital, others, undescribed

<Efficacy endpoints>

Data	Layer separation	
DAS28-4ESR	High Moderate Low Remission	> 5.1 > 3.2 and ≤ 5.1 ≥ 2.6 and ≤ 3.2 < 2.6
DAS28-4CRP	High Moderate Low Remission	> 5.1 > 3.2 and ≤ 5.1 ≥ 2.6 and ≤ 3.2 < 2.6
CDAI	High Moderate Low Remission	> 22.0 > 10.0 and ≤ 22.0 > 2.8 and ≤ 10.0 ≤ 2.8
SDAI	High Moderate Low Remission	> 26.0 > 11.0 and ≤ 26.0 > 3.3 and ≤ 11.0 ≤ 3.3
HAQ-DI	High Moderate Low Remission	> 1.5 > 1.0 and ≤ 1.5 > 0.5 and ≤ 1.0 ≥ 0 and ≤ 0.5
mTSS	Change (≤ 0) Change (≤ 0.5) Change (≤ 1.0)	Change ≤ 0 Change ≤ 0.5 Change ≤ 1.0
Bone erosion score	Change (≤ 0) Change (≤ 0.5) Change (≤ 1.0)	Change ≤ 0 Change ≤ 0.5 Change ≤ 1.0
Joint space narrowing score	Change (≤ 0) Change (≤ 0.5) Change (≤ 1.0)	Change ≤ 0 Change ≤ 0.5 Change ≤ 1.0

*Hereafter, “complete remission” refers to “Remission” in the above table.

12. Handling of data on test/evaluation time

For data entered at each timing of efficacy evaluation excluding mTSS, bone erosion score and joint space narrowing score, the acceptability of data by timing should be judged based on the acceptable range of the timing. The acceptable range of the timing is shown in the table below.

If there is more than one data within the acceptable range of the timing, the data on the closest date to the reference date should be adopted. If there is more than one data within the acceptable range of the timing with the equal number of days from the reference before and after the reference date respectively, the data before the reference date should be adopted.

When evaluating efficacy regarding administration of Humira, it should follow the following provision for the data included in the following acceptable range.

- The data up to the date of final Humira treatment + 28 days should be tabulated.

However, the date of final Humira treatment +28 days is later than the date of survey discontinuation, the data up to the date of survey discontinuation should be tabulated.

This date is called [final evaluation date] in the following.

Timing and period category	Handling of data

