- If the date up to the date of final Humira treatment +56 days, and the date of survey discontinuation is later than the date of survey discontinuation +56 days, the data up to the date of survey discontinuation should be tabulated.

Timing and period category	Handling of data
Prior to treatment start	Data included in the period between the date of initial Humira treatment -56 days and the date of initial Humira treatment +56 days and the closest data to the date of initial Humira treatment should be adopted.
At week 52	Data included in the period between the date of initial Humira treatment +308 days and the date of initial Humira treatment +420 days and the closest data to the date of initial Humira treatment +364 days should be adopted.
At week 104	Data included in the period between the date of initial Humira treatment +672 days and the date of initial Humira treatment +784 days and the closest data to the date of initial Humira treatment +728 days should be adopted.

The time for evaluation of treatment continuing group and treatment discontinued group in the third CRF should also be allocated separately. For patients whom the final Humira treatment is later than week 52 +4 weeks, the data on the latest date in the third CRF should be used as the data on the final evaluation date. However, if there is the date of survey discontinuation, the data up to the date should be used.

This date is called [final evaluation date] in the following.

At final evaluation (third CRF)	
When the date of survey discontinuation is not entered: The last data of the patient among the data included in the period between the date of initial Humira treatment +504 days and the final evaluation date should be adopted.
 
When the date of survey discontinuation is entered: The last data of the patient among the data included in the period between the date of initial Humira treatment +504 days and the final evaluation date should be adopted.

---------------------------------	---

	In the treatment discontinued group, the data of which the date of treatment discontinuation and the final evaluation date are ≥ 24 weeks apart should be adopted.
--	---

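### The survey-discontinuation cut-off for week 52 and week 104 X-ray data (SAP section 12) cannot operate as written, and it is unclear whether the +56-day limit stands alone

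*SAP*

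**What the plan says.** SAP section 12 has two parallel data limits, each applied on top of the visit windows.

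- **Clinical scores.** The base limit has its own sentence: "The data up to the date of final Humira treatment + 28 days should be tabulated". An override follows: where "the date of final Humira treatment +28 days is later than the date of survey discontinuation", the data stop at survey discontinuation.
- **mTSS, bone erosion and joint space narrowing.** Base limit and override are merged into one sentence. It opens "If the date up to the date of final Humira treatment +56 days", adds the condition that "the date of survey discontinuation is later than the date of survey discontinuation +56 days", and ends "the data up to the date of survey discontinuation should be tabulated".

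SAP section 10.1 takes the survey discontinuation date from the third CRF and defines it thus: "It should be the start date of treatment with other biological products, or the older date among the last follow-up date". Protocol section 7.5 ends a patient's participation after week 52 at this point: "When any biologics other than adalimumab is administered". Within the first 52 weeks it ends earlier: "When adalimumab treatment is discontinued".

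Further on, SAP section 12 gives a separate rule for the final X-ray evaluation in the third CRF. Where a survey discontinuation date exists, only data up to that date are used.

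**The concern.** The X-ray override names the same date on both sides of its comparison, so it cannot trigger. The first clause of the sentence has no main verb, so a programmer cannot tell whether the 56-day limit is a rule in its own right or part of the failed condition.

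This sentence is what should keep post-switch films out of the week 52 and week 104 structural results (Tables 6.9.1.1 and 6.9.1.2, the 6.9.3 to 6.9.6 series, and the 6.10 and 6.11 series). mTSS is a named secondary variable. Two programmers working from this text could select different films, and some structural change could be credited to adalimumab although the patient had already started another biologic.

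**Working it through.** The plan gives no figure to reproduce here. The check is one of logic and dates.

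**Inputs**, in days from first Humira treatment:
- H = last Humira treatment; D = survey discontinuation, taken here as the start of another biologic; X = X-ray date.
- X-ray windows (SAP section 12): week 52 is days 308 to 420 (364 ± 56); week 104 is days 672 to 784 (728 ± 56).
- Assumption: H lies between 364 and 728, because D comes from the third CRF, which concerns patients followed past week 52.
- Assumption: D is at least H + 1. SAP section 10.1 moves the last Humira date back one day if it coincides with the start of the other biologic.

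**Step 1, the condition.** D > D + 56 reduces to 0 > 56, which is false for every D. By contrast, the clinical-score condition, H + 28 > D, compares two different dates and is true whenever the switch comes within 28 days of the last Humira treatment.

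**Step 2, the possible readings of the X-ray sentence.**
1. The whole sentence is a single condition. It never triggers, so only the visit window limits X.
2. The 56-day limit stands and only the override fails: X ≤ H + 56.
3. The rule parallels the one for clinical scores: X ≤ min(H + 56, D).

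**Step 3, the longest time from switch to film, X − D.**
- Reading 1: week 52, 420 − 365 = 55 days; week 104, 784 − 365 = 419 days.
- Reading 2: X − D ≤ (H + 56) − (H + 1) = 55 days in either window.
- Reading 3: X ≤ D, so no post-switch film is kept.

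Enumerating every combination of H from 364 to 728, D after H, and X after D inside the window gives:

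| Post-switch date combinations kept | Week 52 | Week 104 |
|---|---|---|
| Reading 1 | 29,260 | 7,497,854 |
| Reading 2 | 29,260 | 146,300 |
| Reading 3 | 0 | 0 |

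These are possible date patterns, not patients. Readings 1 and 2 agree at week 52 because H + 56 is then at least 420, the end of the window.

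**Step 4, relative size under reading 2.** At most 55/364 = 15.1% of the nominal interval from baseline to week 52, and 55/728 = 7.6% of the interval to week 104. The week 52 maximum needs a switch at day 365 and an adopted film at day 420, although the SAP selects the film closest to day 364.

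**The case against.** The strongest reply is that this is a drafting or translation slip whose meaning is plain from the clinical-score rule in the same section. That rule is itself imperfect: its override lacks the word *if*. This has force, and nothing suggests a deliberate analytic choice. But the clinical-score sentence compares two different dates and can be carried out once the missing word is supplied. The X-ray sentence needs one of its dates replaced and its base limit separated out.

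The second reply is that exposure is narrow, and this stands. Protocol section 7.5 ends observation at a switch after week 52, and at discontinuation of adalimumab before then, so post-switch films may seldom be recorded. The survey discontinuation date exists only in the third CRF.

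The different allowances for clinical scores and X-rays (28 and 56 days) are not part of the defect. Only the missing override is.

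A reader might infer that X-rays taken after a switch are never cut off. The documents do not support that. The final X-ray evaluation in the third CRF (the last observation in Table 6.9.2) stops at survey discontinuation under its own rule, and a 56-day limit may still apply to the week 52 and week 104 windows.

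**Conclusion.** The point holds in a limited form. As written, the survey-discontinuation cut-off for the week 52 and week 104 windows of mTSS, bone erosion and joint space narrowing has no effect, and the standing of the 56-day limit is ambiguous. Post-switch films could be tabulated under adalimumab: up to 55 days after the switch if that limit operates, and up to 419 days at week 104 if it does not. Both bounds rest on the assumptions about H and D stated with the calculation.

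It would be tempting to say that about 15% of the interval between readings is spent on another drug. That is only the extreme week 52 case; for week 104 the corresponding maximum is about 8% (55/728), and both figures presuppose that the 56-day limit applies. Nor do the documents show that any result is biased: they give no number of switchers or of films taken after a switch. The primary endpoint, DAS28 below 2.6 at week 52, follows the clinical-score rule and is unaffected. This is a minor but definite correction to a data-selection rule for a secondary endpoint.

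**What to change.** Replace the sentence with two, on the model of the clinical-score rule. First, X-ray data are tabulated through 56 days after the last Humira treatment date. Second, if that limit falls later than the survey discontinuation date, X-ray data are tabulated only through the survey discontinuation date. Under this wording no post-switch film is kept in either window.

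Then confirm that the program for the week 52 and week 104 X-ray tables applies this rule. If it applied another, report how many films change status. The cost is a short SAP text change and a program check; no data collection or clinical procedure is affected.

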7.0 Study Objective (s)

In daily clinical setting, patients with RA who receive adalimumab (Humira[®]) and high-dose MTX (≥ 12 mg/week) will be observed prospectively and the effectiveness will be assessed by DAS28 and mTSS. In addition the safety of the combination of adalimumab and high dose MTX will be assessed in terms of the incidence and pattern of the occurrence of adverse events.

The primary objective of the study is to assess the clinical effectiveness of adalimumab in combination with high dose MTX (≥ 12 mg/week). This will be measured by assessing the percentage of patients with the DAS28 score of < 2.6 at week 52.

The secondary objective of the study is to assess the clinical effectiveness of adalimumab in combination with high dose MTX (≥ 12 mg/week) by assessing the proportion of patients with a change in the following variables from baseline to week 104:

- Clinical Disease Activity Index (CDAI)
-

- Simplified Disease Activity Index (SDAI)
- The severity of functional impairment (HAQ)
- The health-related quality of life (EQ-5D)
- The inhibition of structural progression will be assessed by measuring the modified Van der Heijde Total Sharp Score (mTSS).

The safety profile will be assessed by measuring the following variables:

- All serious adverse events (SAEs) and adverse events (AEs)

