Prior to treatment start	Data included in the period between the date of initial Humira treatment -28 days and the date of initial Humira treatment and the closest data to the date of initial Humira treatment should be adopted.
At week 12	Data included in the period between the date of initial Humira treatment +56 days and the date of initial Humira treatment +112 days and the closest data to the date of initial Humira treatment +84 days should be adopted.
At week 24	Data included in the period between the date of initial Humira treatment +140 days and the date of initial Humira treatment +196 days and the closest data to the date of initial Humira treatment +168 days should be adopted.
At week 52	Data included in the period between the date of initial Humira treatment +336 days and the date of initial Humira treatment +392 days and the closest data to the date of initial Humira treatment +364 days should be adopted.
At week 76	Data included in the period between the date of initial Humira treatment +504 days and the date of initial Humira treatment +560 days and the closest data to the date of initial Humira treatment +532 days should be adopted.
At week 104	Data included in the period between the date of initial Humira treatment +700 days and the date of initial Humira treatment +756 days and the closest data to the date of initial Humira treatment +728 days should be adopted.
At final evaluation	The final data of the patient among the data included in the period between the date of initial Humira treatment +1 day and the final evaluation date should be adopted.

For data entered at each evaluation timing of mTSS, bone erosion score and joint space narrowing score when evaluating efficacy regarding administration of Humira, the acceptability of data by timing should be judged based on the acceptable range of the timing. The acceptable range of the timing is shown in the table below.

If there is more than one data within the acceptable range of the timing, the data on the closest date to the reference date should be adopted. If there is more than one data within the acceptable range of the timing with the equal number of days from the reference before and after the reference date respectively, the data before the reference date should be adopted.

Additionally, it should follow the following provision for the data included in the following acceptable range.

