Analysis object: Patients included in the efficacy analysis set (mTSS in the third CRF)

Purpose of analysis: To categorize the patients by the continuing group and the discontinued group, indicate the number of patients by evaluation time and the summary statistics of the score and the response for mTSS, and conduct a paired t test for the response from baseline. Additionally, the number and percentage of the patients by evaluation time by mTSS category should be shown. The mTSS category should follow “11. Data-layer separation.”

Note: Continuing group...

Corresponding to the definition of the treatment continued group in “10. Derivation and calculation methods”

Discontinued group...

Corresponding to the definition of the treatment discontinued group in “10. Derivation and calculation methods”

Last observation...

Corresponding to the definition of the final evaluation time in “12. Handling of data on test/evaluation time (third CRF).”

“Table 6.9.3.1 mTSS Remission Rate at Week 52”

Analysis object: Patients included in the efficacy analysis set (mTSS at week 52)

Purpose of analysis: To indicate the number and percentage of patients who achieved the mTSS change (≤ 0.5 , ≤ 0 , ≤ 1) at week 52, respectively. In addition, the distribution of mTSS changes at week 52 as the Y axis and mTSS change at week 52 of which the percentage of the patients analyzed with the mTSS change in the ascending order as the X axis should also be illustrated.

Note: This form should be prepared only at the time of literature analysis.

“Table 6.9.3.2 mTSS Remission Rate at Week 104”

Analysis object: patients included in the efficacy analysis set (mTSS at week 104)

Purpose of analysis: To indicate the number and percentage of patients who achieved the mTSS changes (≤ 0.5 , ≤ 0 , ≤ 1) at week 104, respectively. In addition, the distribution of mTSS change at week 104 as the Y axis and mTSS changes at week 104 of which the percentage of the patients analyzed with the mTSS change in the ascending order as the X axis should also be illustrated.

Note: This form should be prepared only at the time of literature analysis.

“Table 6.9.4.1 Correlation of Subjective background (Spearman's rank correlation coefficient) at the mTSS Remission by Week 52”

Analysis object: Patients included in the efficacy analysis set (mTSS at week 52)

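### The mTSS baseline may be a film taken up to 56 days after the first dose, and raw change is cut at 0, 0.5 and 1.0 with no account of the interval between films

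*SAP*

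**What the plan says.** Protocol section 7.0 lists structural damage among the secondary objectives: "The inhibition of structural progression will be assessed by measuring the modified Van der Heijde Total Sharp Score (mTSS"). Protocol Table 1 schedules X-rays at weeks 0, 52 and 104, and section 7.6.2 adds that items are recorded only where routine care produces them.

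SAP section 12 sets the film windows:

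- **Baseline**, in a row labelled as pre-treatment: "Data included in the period between the date of initial Humira treatment -56 days and the date of initial Humira treatment +56 days".
- **Week 52**: between "the date of initial Humira treatment +308 days and the date of initial Humira treatment +420 days".
- **Week 104**: between "the date of initial Humira treatment +672 days and the date of initial Humira treatment +784 days".
- **Several films in one window**: "the data on the closest date to the reference date should be adopted". The earlier film takes precedence only on an exact tie.

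For the clinical scores the same section uses a different baseline: "Data included in the period between the date of initial Humira treatment -28 days and the date of initial Humira treatment and the closest data". No post-dose value can serve there.

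SAP section 10.3 derives mTSS as the mean of two readers, without time scaling. SAP section 11 cuts the change as "Change (≤ 0) Change (≤ 0.5) Change (≤ 1.0"). These cuts, or the same raw change, feed Tables 6.9.1.1 to 6.11.2, including the logistic models in Tables 6.9.5.1 to 6.9.6.2. Listing 8.1 labels a change of 0 or less as no progression and 0.5 or less as structural remission. Neither document reports the film interval, adjusts for it, or plans an analysis limited to pre-dose baseline films.

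**The concern.** Joint damage accrues over time, so a change score means little without its interval. Two features of the windows loosen that link.

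First, a film taken eight weeks into treatment can stand as baseline. Patients enter with DAS28-CRP above 3.2, so disease is active, and any damage in those weeks is absorbed into the baseline and cannot count as progression. Where a patient has films at day -20 and day +15, the closest-date rule takes the post-dose one.

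Second, patients with quite different observation times are judged against the same cut. With a single arm, no comparator shares and cancels that effect. If the interval happens to be related to a patient factor, the mTSS predictor models could attribute timing to that factor. Table 6.9.2 sets continuing and discontinued groups side by side using a last film from day 504 onward. The discontinued group must also have at least 24 weeks between stopping Humira and the film, so intervals may differ between the two groups.

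**Working it through.** The plan gives no figure for the film interval, so there is none to reproduce. The inputs are the SAP section 12 windows (baseline -56 to +56; week 52 at 308 to 420; week 104 at 672 to 784; reference days 364 and 728).

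**Range of intervals.** Shortest = earliest follow-up day minus latest baseline day. Longest = latest follow-up day minus earliest baseline day.

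| | Shortest | Longest | Ratio | Share of nominal |
|---|---|---|---|---|
| Week 52 | 308 - 56 = 252 d | 420 + 56 = 476 d | 1.89 | 69% to 131% |
| Week 104 | 672 - 56 = 616 d | 784 + 56 = 840 d | 1.36 | 85% to 115% |
| Week 52, baseline at day 0 or earlier | 308 d | 476 d | 1.55 | 85% to 131% |
| Clinical scores, week 52 | 336 - 0 = 336 d | 392 + 28 = 420 d | 1.25 | 92% to 115% |

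The post-dose allowance therefore explains only part of the week-52 spread. The data cut-off sentence just before the mTSS table compares the survey discontinuation date with itself plus 56 days, so it does not clearly narrow these windows.

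**What the cut means as a rate.** Rate per 364 days = cut × 364 / interval. For 0.5 this is 0.5 × 364 / 252 = 0.72 at the shortest week-52 interval and 0.5 × 364 / 476 = 0.38 at the longest. For 1.0 it is 1.44 and 0.76.

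**A less extreme case.** Baseline at day 56 and follow-up on schedule at day 364 give 308 days, a loss of 56 / 364 = 15%.

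**Effect on the shares (illustration).** The documents give no progression rate, so the rates here are assumed. Suppose new damage arrives as a Poisson process in steps of 0.5, the step size when integer scores from two readers are averaged, with no negative changes. With λ = rate × (days / 364) / 0.5, P(change ≤ 0) = exp(-λ) and P(change ≤ 0.5) = exp(-λ)(1 + λ).

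| Assumed rate per 364 d | Share | 252 d | 308 d | 364 d | 476 d |
|---|---|---|---|---|---|
| 0.25 | ≤ 0 | 71% | 66% | 61% | 52% |
| 0.25 | ≤ 0.5 | 95% | 93% | 91% | 86% |
| 0.5 | ≤ 0 | 50% | 43% | 37% | 27% |
| 0.5 | ≤ 0.5 | 85% | 79% | 74% | 62% |
| 1.0 | ≤ 0 | 25% | 18% | 14% | 7% |
| 1.0 | ≤ 0.5 | 60% | 50% | 41% | 26% |

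Each column treats every patient as having that interval. In this model, a day-56 baseline alone raises the share at or below 0.5 by 2 to 9 percentage points for the patients it applies to.

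**Why the cuts should not be moved to an annualised change.**

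- Dividing by a positive number cannot change the sign, so the class at or below 0 is unaltered.
- An on-schedule change of 0.5 becomes 0.5 × 365 / 364 = 0.5014 and falls outside the cut.
- At week 104 a raw change of 1.0 passes the 0.5 cut from 730 days (1.0 × 365 / 730 = 0.5; at 840 days it is 0.43), which is a laxer endpoint than the SAP's.

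**The case against.** The strongest reply is that a wide film window is a sensible choice in routine care. X-rays may not fall on the day of the first dose, joint damage moves more slowly than a clinical score, and a stricter window would lose patients. That stands: the difference from the clinical-score baseline is not in itself an error, and post-dose films should remain usable where nothing better exists.

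The extremes of 252 and 476 days need both films at opposite window edges, and the closest-date rule matters only for patients with more than one baseline film, whereas the schedule plans one. Both points stand, and they limit the size that can be claimed.

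A reader might infer that the windows inflate the share without worsening. The documents do not support that. The windows are symmetric around their reference days; a post-dose baseline or early follow-up film shortens the interval, while an early baseline or late follow-up film lengthens it. A reader might also infer that film timing differs by site. Neither document says so; with about 100 routine-care sites it is a possibility to check.

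Finally, mTSS is secondary, the mTSS tables also give summary statistics and paired t tests, and Tables 6.9.3.1 and 6.9.3.2, the week-52 logistic models and listing 8.1 are reserved for the literature analysis. That lowers the stakes, but a stated objective still rests on these changes.

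**Conclusion.** The point holds in a limited form. The baseline row's label and its window disagree, since the window accepts films to day +56. Film intervals can span 252 to 476 days for week 52 and 616 to 840 days for week 104, and fixed cuts on raw change are read with no account of this. For an individual patient, a post-dose baseline favours no worsening. For the study as a whole, neither direction nor size can be stated without the film dates; the percentages above rest on assumed rates and a Poisson model. A patient with no progression is unaffected by timing. DAS28 remission at week 52 and the sample size are untouched. This is an inexpensive improvement to a secondary endpoint.

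**What to change.** In SAP section 12, take as mTSS baseline the closest film on or before the first dose, within 56 days. Use a post-dose film (to day +56) only if there is none, and report how many patients have one. Then:

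1. Keep the raw cut-points as the main reading in Tables 6.9.1.1 to 6.11.2.
2. Add a sensitivity analysis limited to patients with a pre-dose baseline film.
3. Tabulate the distribution of film intervals, overall and for the continuing and discontinued groups of Table 6.9.2.
4. Include film interval as a covariate in the mTSS logistic models (Tables 6.9.5.1 to 6.9.6.2).
5. If a rate is shown, give mean change scaled to the nominal interval (364 days for week 52, 728 for week 104) beside the raw change. Do not apply the 0, 0.5 and 1.0 cuts to an annualised value.

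The windows already require film dates, so no new films or readings are needed. The cost is SAP wording, some extra tabulation, and a smaller n in the pre-dose-only analysis. For some patients the chosen film will be earlier and the interval longer: replacing day +15 by day -20 adds 35 days. Because the pre-dose-only analysis still allows 308 to 476 days at week 52, the interval table is needed as well.
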